14.4.2. Reporting Standards

General

- The current GSK Integrated Data Standards Library (IDSL) will be applied for reporting, unless otherwise stated (IDSL Standards Location:
 - https://spope.gsk.com/sites/IDSLLibrary/SitePages/Home.aspx):
- Under Supporting Documentation > Component > Statistical Displays
 - 4.03 to 4.23: General Principles
 - 5.01 to 5.08: Principles Related to Data Listings
 - 6.01 to 6.11: Principles Related to Summary Tables
 - 7.01 to 7.13: Principles Related to Graphics
- Do not include subject level listings in the main body of the GSK Clinical Study Report. All subject level listings should be located in the modular appendices as ICH or non-ICH listings

Formats

- GSK IDSL Statistical Principles (5.03 & 6.06.3) for decimal places (DP's) will be adopted for reporting of data based on the raw data collected, unless otherwise stated.
- Numeric data will be reported at the precision collected on the eCRF.
- The reported precision from non eCRF sources will follow the IDSL statistical principles but may be adjusted to a clinically interpretable number of DP's.

Planned and Actual Time

- Reporting for tables, figures and formal statistical analyses:
 - Planned time relative to dosing will be used in figures, summaries, statistical analyses and calculation of any derived parameters, unless otherwise stated.
 - The impact of any major deviation from the planned assessment times and/or scheduled visit days on the analyses and interpretation of the results will be assessed as appropriate.
- Reporting for Data Listings:
 - Planned and actual time relative to study drug dosing will be shown in listings (Refer to IDSL Statistical Principle 5.05.1).
 - Unscheduled or unplanned readings will be presented within the subject's listings.

Unscheduled Visits									
 Unscheduled visit 	ts will not be included in by-visit summary tables and figures.								
 Unscheduled visit 	ts will be considered when deriving maximum/worse post-baseline values.								
All unscheduled v	All unscheduled visits will be included in listings.								
Descriptive Summary Statistics									
Continuous Data Refer to IDSL Statistical Principle 6.06.1									
Categorical Data N, n, frequency, %									
Graphical Displays									
Refer to IDSL Sta	tistical Principals 7.01 to 7.13.								
Laboratory Paramete	ers								
detectable level re character value st	If a laboratory value which is expected to have a numeric value for summary purposes, has a non- detectable level reported in the database, where the numeric value is missing, but typically a character value starting with ' <x' '="" or="">x' (or indicated as less than x or greater than x in the comment field) is present, the number of significant digits in the observed values will be used to determine how</x'>								

Example 1: 2 Decimal Places= '< x ' becomes x – 0.01

much to add or subtract in order to impute the corresponding numeric value.

- O Example 2: 1 Decimal Place= '> x' becomes x + 0.1
- Example 3: 0 Decimal Places= '< x' becomes x 1

14.4.3. Reporting Standards for Pharmacokinetic

Concentration Data	
Descriptive	Refer to IDSL Statistical Principle 6.06.1
Summary Statistics	Assign zero to NQ values (Refer to GUI_51487 for further details)
Pharmacokinetic Para	ameters
Descriptive Summary Statistics (Log Transformed)	N, n, geometric mean, 95% CI of geometric mean, standard deviation (SD) of logged data and [between and or within] geometric coefficient of variation (CVb/w (%)) will be reported. [1] CV_b (%) = $\sqrt{\exp(SD^2) - 1} * 100$ (SD = SD of log transformed data) [2] CV_w (%) = $\sqrt{\exp(MSE) - 1} * 100$ (MSE = mean square error from mixed effect model of loge-transformed data).
Parameters Not Being Log Transformed	tmax, tlast

14.5. Appendix 5: Reporting Standards for Missing Data

14.5.1. Handling of Missing Data

Element	Reporting Detail
General	Missing data occurs when any requested data is not provided, leading to blank fields on the collection instrument:
	 These data will be indicated by the use of a "blank" in subject listing displays. Unless all data for a specific visit are missing in which case the data is excluded from the table.
	 Answers such as "Not applicable" and "Not evaluable" are not considered to be missing data and should be displayed as such.
Outliers	Any participants excluded from the summaries and/or statistical analyses will be documented along with the reason for exclusion in the clinical study report.

14.5.1.1. Handling of Missing and Partial Dates

Element	Reporting Detail
General	Partial dates will be displayed as captured in subject listing displays.
Adverse Events	 The eCRF allows for the possibility of partial dates (i.e., only month and year) to be recorded for AE start and end dates; that is, the day of the month may be missing. In such a case, the following conventions will be applied for calculating the time to onset and the duration of the event: Missing Start Day: First of the month will be used unless this is before the start date of study treatment; in this case the study treatment start date will be used and hence the event is considered as treatment-emergent. Last day of the month will be used, unless this is after the stop date of study treatment; in this case the study treatment stop date will be used. Completely missing start or end dates will remain missing, with no imputation applied. Consequently, time to onset and duration of such events will be missing. Start or end dates which are completely missing (i.e. no year specified) will remain missing, with no imputation applied.
Concomitant Medications/Medical History	 Partial dates for any concomitant medications recorded in the CRF will be imputed using the following convention: If the partial date is a start date, a '01' will be used for the day and 'Jan' will be used for the month If the partial date is a stop date, a '28/29/30/31' will be used for the day (dependent on the month and year) and 'Dec' will be used for the month. The recorded partial date will be displayed in listings.

14.6. Appendix 6: Values of Potential Clinical Importance

14.6.1. Laboratory Values

Haematology				
Laboratory Parameter	Units	Category	Clinical Concern Range	
			Low Flag (< x)	High Flag (>x)
		Male		0.54
Hematocrit	Ratio of 1	Female		0.54
		Δ from BL	↓0.075	
	a/I	Male		180
Hemoglobin	g/L	Female		180
		Δ from BL	↓25	
Lymphocytes	x109/ L		0.8	
Neutrophil Count	x109/ L		1.5	
Platelet Count	x10 ⁹ / L		100	550
While Blood Cell Count (WBC)	x10 ⁹ / L		3	20

Clinical Chemistry				
Laboratory Parameter	Units	Category	Clinical Concern Range	
-			Low Flag (< x)	High Flag (>x)
Albumin	mmol/L		30	
Calcium	mmol/L		2	2.75
Creatinine	mmol/L	Δ from BL		↑ 44.2
Glucose	mmol/L		3	9
Magnesium	mmol/L		0.5	1.23
Phosphorus	mmol/L		0.8	1.6
Potassium	mmol/L		3	5.5
Sodium	mmol/L		130	150
Total CO2	mmol/L		18	32

Liver Function			
Test Analyte	Units	Category	Clinical Concern Range
ALT/SGPT	U/L	High	≥ 2x ULN
AST/SGOT	U/L	High	≥ 2x ULN
AlkPhos	U/L	High	≥ 2x ULN
T Bilirubin	µmol/L	High	≥ 1.5xULN
	µmol/L		1.5xULN T. Bilirubin
T. Bilirubin + ALT		High	+
	U/L		$\geq 2x$ ULN ALT

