14.9.13. ICH Listings

ICH: Lis	CH: Listings							
No.	Population	IDSL / Example Shell	Title	Programming Notes	Deliverable			
1.	Safety	DM2	Listing of demographic characteristics for healthy volunteers		IA1			
2.	Safety	DM2	Listing of demographic characteristics for psoriasis patients		IA2 W2			
3.	Safety	AE7	Listings of subject numbers for individual adverse events for healthy volunteers		SAC			
4.	Safety	AE7	Listings of subject numbers for individual adverse events for psoriasis patients	same as for HV	IA2 W2			
5.	Safety	CP_AE8	Listing of all adverse events for healthy volunteers		IA2 W2			
6.	Safety	CP_AE8	Listing of all adverse events for psoriasis patients	same as for HV	IA2 W2			
7.	Safety	CP_AE8a	Listing of serious adverse events for healthy volunteers	Same as for all Aes	IA2 W2			
8.	Safety	CP_AE8a	Listing of serious adverse events for psoriasis patients	same as for HV	IA2 W2			
9.	Safety	CP_AE8	Listing of adverse events leading to withdrawal from study for healthy volunteers		SAC			
10.	Safety	CP_AE8	Listing of adverse events leading to withdrawal from study for psoriasis patients		SAC			
11.	Safety	CP_LB5	Listing of clinical chemistry abnormalities of potential clinical importance for healthy volunteers		IA2 W2			
12.	Safety	CP_LB5	Listing of clinical chemistry abnormalities of potential clinical importance for psoriasis patients		IA2 W2			
13.	Safety	CP_LB6	Listing of all clinical chemistry laboratory data for subjects with PCI abnormalities for healthy volunteers		IA1 SAC			

ICH: Lis	ICH: Listings					
No.	Population	IDSL / Example Shell	Title	Programming Notes	Deliverable	
14.	Safety	CP_LB6	Listing of all clinical chemistry laboratory data for subjects with PCI abnormalities for psoriasis patients		IA2 W2	
15.	Safety	CP_LB5	Listing of haematology abnormalities of potential clinical importance for healthy volunteers		IA2 W2	
16.	Safety	CP_LB5	Listing of haematology abnormalities of potential clinical importance for psoriasis patients		IA2 W2	
17.	Safety	CP_LB6	Listing of all haematology laboratory data for subjects with PCI abnormalities for healthy volunteers		SAC	
18.	Safety	CP_LB6	Listing of all haematology laboratory data for subjects with PCI abnormalities for psoriasis patients		IA2 W2	
19.	Safety	UR2a	Listing of urinalysis data for healthy volunteers		IA1 SAC	
20.	Safety	UR2a	Listing of urinalysis data for psoriasis patients		SAC	
21.	Safety		Listing of CMV and EBV serology for healthy volunteers		SAC	

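### SAP 14.6.1 prints the creatinine and albumin clinical-concern limits in mmol/L, a unit in which neither limit can work

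*SAP*

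**What the plan says.** The clinical chemistry part of SAP 14.6.1 gives every analyte in mmol/L. Two rows matter here:

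- Creatinine is assessed as change from baseline. The row reads "Creatinine mmol/L" and the high-flag limit is a rise of 44.2.
- Albumin has a low-flag limit only; the row reads "Albumin mmol/L 30".

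The column headings fix the direction of comparison: "Low Flag (< x) High Flag (>x").

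Other parts of the same section use other units. The liver table has "T Bilirubin µmol/L" and the haematology table has "Hemoglobin g/L".

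The limits feed the ICH listings in SAP 14.9.13. Listing 11 is the "Listing of clinical chemistry abnormalities of potential clinical importance for healthy volunteers", and listing 12 is its counterpart for psoriasis patients. Listings 13 and 14 give all chemistry data for subjects who have at least one such abnormality.

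No other section of either document gives a unit for creatinine or albumin. Protocol 6.3.7 only names the analytes, and protocol 5.6.3 uses a relative rise in creatinine of at least 30%.

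**The concern.** A flag is useful only if some plausible results fall on each side of its limit. In mmol/L, no plausible creatinine rise lies above 44.2 and no plausible albumin result lies above 30. Read literally, the first flag is always off and the second always on.

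Safety is the primary objective and laboratory data are among the primary endpoints (protocol section 2, SAP 2.2). Protocol Table 5 names immune-complex deposition in the kidney as a potential risk and includes chemistry among the tools for watching renal function. A listing that cannot show a creatinine rise, or one that selects everybody because of albumin, would not do its job in the study report.

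**Working it through.** The plan gives no derivation of these limits, so there is no figure to reproduce. The check is a conversion of units.

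**Inputs from the SAP (14.6.1):** creatinine rise > 44.2 mmol/L; albumin < 30 mmol/L.

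**Assumptions, not in the documents:** molar mass of creatinine 113.12 g/mol; molar mass of serum albumin 65,000 to 69,000 g/mol; baseline creatinine 50 to 120 µmol/L, with 2,000 µmol/L as a deliberate extreme; serum albumin 20 to 60 g/L, chosen wide.

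**Creatinine as written**

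- 44.2 mmol/L × 1,000 = 44,200 µmol/L.
- In mass units: 44.2 × 113.12 / 10 ≈ 500 mg/dL.
- Rise required as a multiple of baseline: 44,200 / 120 ≈ 368; 44,200 / 50 = 884; at the extreme, 44,200 / 2,000 ≈ 22.

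No subject could reach this, so the flag cannot fire.

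**Albumin as written**

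- 30 mmol/L = 0.030 mol/L × 65,000 to 69,000 g/mol = 1,950 to 2,070 g/L.
- Lowest assumed result: 20 / 69,000 × 1,000 ≈ 0.29 mmol/L.
- Highest assumed result: 60 / 65,000 × 1,000 ≈ 0.92 mmol/L.

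Every result is far below 30 mmol/L, so the flag always fires.

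**The same numbers in the units that their size suggests**

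| Limit | Unit tried | Equivalent | Can it discriminate? |
|---|---|---|---|
| Creatinine rise > 44.2 | µmol/L | about 0.50 mg/dL; 88% of a baseline of 50, 55% of 80, 37% of 120 µmol/L | Yes |
| Albumin < 30 | g/L | 0.43 to 0.46 mmol/L | Yes, inside the assumed 20 to 60 g/L |

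Against these readings the printed creatinine limit is 1,000 times too high and the printed albumin limit 65 to 69 times too high.

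**Is it an artefact of reading the PDF?** Some entries in the units column of the haematology table are damaged. But µmol/L comes through intact for bilirubin and g/L for haemoglobin in the same section, and g/L could not plausibly be misread as mmol/L. A single unit filled down the chemistry column is the more likely cause, though that is an inference.

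**The case against.** The strongest reply is that the SAP describes no conversion of laboratory results into the printed units; it refers only to the sponsor's data standards. If the laboratory data are held in µmol/L and g/L and the program compares bare numbers, both flags behave as intended and the fault is one of labelling. This stands. The documents do not give the dataset units, so the effect on the listings is conditional.

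A second reply is that renal safety does not depend on this table. This also stands. The creatinine criterion in protocol 5.6.3 is a relative rise and has no unit. Protocol Table 5 adds physical examination and urinalysis. SAP Tables 3.12 to 3.15 show chemistry values and changes by visit without using the limits, and urinalysis has its own tables (3.20, 3.21) and listings (19, 20). A reader might infer that renal monitoring in the trial is disabled; the documents do not support that. These are reporting flags, and the exposure is limited to the creatinine and albumin entries in listings 11 to 14.

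Third, an albumin failure would be conspicuous: listings 11 and 12 are due at the second wave of interim 2, and SAP 14.9.3 provides for review of those outputs before the final re-run list is settled. That helps less for creatinine, because flags that never appear attract no attention.

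Fourth, the intended units are inferred from the size of the limits. That is correct, and it is why the fix includes a confirmation step.

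**Conclusion.** The two unit cells are wrong as written: neither limit is usable in mmol/L. The finding does not depend on the exact molar masses or on the assumed ranges of results, because the margins are so large.

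The consequence depends on programming. If results are held in or converted to the stated unit, listings 11 and 12 would contain no creatinine rise and every albumin result, and listings 13 and 14 would include every subject with an albumin result and so lose their selective purpose. If bare numbers are compared with data in µmol/L and g/L, nothing in the output changes except the printed unit. A reader might infer flag rates of 0% and 100% whatever the data; that holds only in the first case, and the SAP alone does not settle which case applies.

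This is a minor correction to the reporting of a primary safety endpoint. It does not affect in-trial monitoring or the by-visit chemistry summaries.

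**What to change.** In SAP 14.6.1, change the unit for creatinine to µmol/L and for albumin to g/L, leaving 44.2 and 30 as they are, once the sponsor has confirmed both units against the laboratory dataset. Then check that the programs for ICH listings 11 to 14 compare results and limits in the same unit. Listing 13 is assigned to the first interim as well as to the final analysis, so any copy already produced should be included in that check.

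The cost is two table cells and one programming check. No analysis, display or clinical rule changes, and there is no downside.

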14.6.2. ECG

ECG Parameter	Units	Clinical Concern Range	
		Lower	Upper
Absolute			
Absolute QTc Interval	msec		> 450
Absolute PR Interval	msec	< 110	> 220
Absolute QRS Interval	msec	< 75	> 110
Change from Baseline			
Increase in Baseline in QTc	msec		>60

The following categories will be used for summarising by:

- the maximum QTc values post-baseline relative to baseline
- the maximum increase in QTc values post-baseline relative to baseline

ECG Parameter	Units	Clinical Concern Range	
		< 450	
Absolute QTcB and QTcF	msec	≥ 450	≤ 479
Interval		≥ 480	≤ 500
		> 500	
0, , , , , ,	msec	< 30	
Change from baseline in QTcB and QTcF		≥ 30	≤ 60
WICD allu WICF		> 60	

14.6.3. Vital Signs

Vital Sign Parameter	Units	Clinical Concern Range	
(Absolute)		Lower	Upper
Systolic Blood Pressure	mmHg	< 85	> 160
Diastolic Blood Pressure	mmHg	< 45	> 100
Heart Rate	bpm	< 40	> 110

14.7. Appendix 7: Pharmacokinetic/Pharmacodynamic Analyses

All non-linear mixed effects modelling will be performed using NONMEM (ICON Solutions), PsN (Perl Speaks NONMEM) and Pirana (Pirana Software & Consulting BV 2016).

R (The R Foundation for Statistical Computing) will be used for exploratory graphical analysis, graphical model diagnostics and, if needed, modifications of the dataset.

The analysis will be performed by, or under the direct auspices of, Clinical Pharmacology Modelling and Simulation (CPMS), GlaxoSmithKline in the GSK modelling environment MAP (Model-based Analyses Platform) using the currently supported versions of all software packages.

14.7.1. Pharmacokinetic / Pharmacodynamic Dataset Specification

The merging of aLAG3, regiment, biomarker and demographic data together with the creation of the NONMEM-specific dataset will be performed by, or under the direct auspices of, Clinical Statistics (Programmer), GlaxoSmithKline.

This dataset programming will be conducted in a HARP environment using the currently supported version of SAS.

14.7.2. Pharmacokinetic / Pharmacodynamic Methodology

An exploratory graphical analysis of the data will be performed by generating the plots as presented in Appendix 9.

Model development will be data driven.

The initial PK model of choice will be a compartmental model with linear and nonlinear drug elimination. Further model testing will include, but it is not limited to, a compartmental model with target mediated drug disposition (TMDD) and a minimal PBPK model with TMDD incorporated. We anticipate TMDD to be driven by soluble LAG3 (sLAG3). However, if data allow, we plan to test also more complex models with TMDD driven by both, sLAG3 and T-cell bound LAG3.

The final PK model, possibly incorporating TMDD, will be used to develop a PK-RO model. Data relative to CD4+CD45RA- cell count will be used to model RO (quantified by J11L1 marker) and T-cell depletion (quantified by 1B4 marker). The initial RO model will likely be an Emax model. More complex models might be investigated if the data support it.

If plots (and summary) of NCA derived PK parameters identified ADA status, and/or HV vs Pso as possible significant covariates, we will investigate the influence of these covariates in the PK and RO models. Other covariates may be explored as appropriate.

CONFIDENTIAL

200630

Model acceptability will be judged by convergence, covariance estimation and standard goodness-of-fit plots that may include, but are not limited to:

- Population and individual predictions versus observations
- Conditional weighted residuals versus population predictions and time

For the final PK and the final RO models visual predictive checks (VPCs) will be conducted to assess graphically whether simulations from the developed models are able to reproduce both the central trend and variability in the observed data from the current study as a function of time.

The VPC will be based on 1000 simulations with the model and the design structure of the observed data (i.e. dose level and time, time of PK sampling and individual values of model covariates, if any). The median and the 10th and 90th will be compared to the observed data. Stratification by dose level of GSK2831781 will be used. Other stratification, such as healthy/ psoriasis will be applied in case these covariates were tested in the model.

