1. INTRODUCTION

1.1. Study Rationale

This study is the first administration of GSK2831781 in humans and will evaluate in two parts the safety, tolerability, pharmacokinetics (PK), pharmacodynamics (PD) and immunogenicity of single intravenous (IV) doses of GSK2831781 administered to healthy volunteers (Part A), including a cohort of those previously vaccinated with Bacillus Calmette Guérin (BCG) (Part A delayed type hypersensitivity [DTH] cohort) and patients with plaque psoriasis (Part B). Single dose escalation will allow for the identification of any immediate dose-limiting toxicities. Investigation of pharmacology in healthy subjects in the Part A DTH cohort will confirm whether the selected dose is likely to result in pharmacodynamic effects in immune-inflammatory diseases associated with the target Lymphocyte Activation Gene 3+ (LAG-3+) T cells, which are then tested in Part B. As there are very low levels of LAG-3+ T cells in blood it is necessary to monitor LAG-3+ cells at the site of antigen challenge or the disease site. The use of a DTH in healthy subjects in Part A allows investigations into the impact of GSK2831781 on immunological endpoints after a controlled challenge. The switch to patients with psoriasis in Part B, at a dose by which effects would be expected, then allows investigations of higher doses in a chronic disease setting. Measuring the pharmacology of GSK2831781 using the depletion of LAG-3+ T cells in skin biopsies from Tuberculin Purified Protein Derivative (PPD) skin challenge and lesional skin biopsies from patients with psoriasis, is an important component of the study and for the latter may enable an understanding of the dose response relationship, which will be important for decision making and the design of future studies in immuno-inflammatory diseases, including psoriasis. The use of DTH and psoriasis subjects to explore the mechanism in biopsies and clinical response endpoints in these populations, as well as investigate systemic biomarkers will also provide useful information before conducting studies in other immune-inflammatory disease where more invasive tissue biopsies would be required.

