6.8.4. LAG-3 Cell Receptor Occupancy

The binding of GSK2831781 to cell surface LAG-3 may be measured (bound and free) using competitive and non-competitive anti-LAG3 antibodies.

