10.3. Other PD parameters

10.3.1. Endpoint / Variables

The following endpoints are of interest (SI dataset: BIOMARK):

- s-LAG3 parameters no derivation is needed
- Flow cytometry 6 key parameters only described below:

Marker code	Marker	Type (BITESTCD)	Unit (BISTRESU)
CDX226	CD45+ CD3- CD19+	Concentration	CELLS/UL
CDX258	CD45+ CD3+ CD69+	Concentration	CELLS/UL
CDX444	CD4+CD45RA+1B4+	Number of events	COUNT
CDX445	CD4+CD45RA+J11L1+	Number of events	COUNT
CDX446	CD4+CD45RA-1B4+	Number of events	COUNT
CDX447	CD4+CD45RA-J11L1+	Number of events	COUNT

For 4 of these endpoints (CDX444, CDX445, CDX446, CDX447), the derivation below should be applied (same derivation as for PK analyses):

The count at each time point is the difference: BISTRESN value in the row with BIEXPS = "Stained Sample - T cell markers including J11 and 1B4" - BISTRESN value in the row with BIEXPS = 'LAG3 FMO Control - T cell markers excluding J11 and 1B4'

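### The four LAG-3 flow markers are unscaled FMO-subtracted event counts shown as percent of baseline with no rule for a non-positive baseline, and receptor occupancy has no formula that separates it from depletion

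*SAP*

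**What the plan says.** **Derivation.** SAP 10.3.1 lists six key flow parameters. Two are concentrations in cells/µL. The other four are numbers of events: 1B4+ and J11L1+ cells, each within CD4+CD45RA+ and CD4+CD45RA-. For these four it says "For 4 of these endpoints (CDX444, CDX445, CDX446, CDX447), the derivation below should be applied". The rule begins "The count at each time point is the difference: BISTRESN value in the row with BIEXPS" and subtracts the LAG3 FMO (fluorescence-minus-one) control row from the stained-sample row. A note that this is the "same derivation as for PK analyses" ties the same quantity to the modelling data.

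**Summary measures.** SAP 10.3.2 asks for the absolute value, change from baseline and percent of baseline, the last being 100 times the post-dose value over baseline. Tables 6.6 and 6.7 show all three. Figures 6.8 and 6.9 plot individual absolute values and percent of baseline. Figures 6.10, 6.11, 6.19 and 6.20 plot the group mean percent of baseline. The baseline rule in SAP 5.2 deals only with a missing baseline.

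**Receptor occupancy (RO).** Protocol 6.8.4 says binding to cell-surface LAG-3 "may be measured (bound and free) using competitive and non-competitive anti-LAG3 antibodies". It does not say which clone is which. SAP 14.7.2 draws on the CD4+CD45RA- counts to model "RO (quantified by J11L1 marker) and T-cell depletion (quantified by 1B4 marker". On the model it adds: "The initial RO model will likely be an Emax model. More complex models might be investigated if the data support it". No equation for RO appears, and no output in SAP Appendix 9 combines the two markers.

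**Abundance.** Protocol 1.1 explains the use of skin sampling with "As there are very low levels of LAG-3+ T cells in blood". Protocol 1.2.2 puts LAG-3+ T cells below 1% in healthy volunteers.

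**The concern.** There are two separate weaknesses.

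The first is in the counts. Subtracting raw events across two tubes is valid only if both tubes acquired the same number of parent cells. Comparing visits on raw events also needs equal acquisition over time. Neither document says that either holds. The net count then becomes a denominator, for a cell type that the protocol calls scarce. A difference of two small counts can be zero or negative. It can also be a very small positive number, which gives an enormous percentage. One such subject can dominate a group mean in an active cohort of six.

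The second is in occupancy. The drug is meant both to bind LAG-3 and to kill the cells that carry it. A stain that detects only free LAG-3 loses events through either route. Unless the J11L1 signal is set against total LAG-3+ cells, occupancy and depletion cannot be told apart. The potency estimate from the PK-RO model would then mix the two. Recovery visits are most exposed. Protocol 3.3.1 expects drug at 5 mg/kg to be below quantitation by Day 85 and raises slow repletion of LAG-3+ cells, and Table 9 samples RO at Days 85 and 121.

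**Working it through.** **1. Effect of unscaled subtraction (assumed counts).** Take 100 stained and 60 FMO events, so net = 40.
- FMO tube acquires 20% fewer parent cells: 60 × 0.8 = 48, net = 52.
- FMO tube acquires 20% more: 60 × 1.2 = 72, net = 28.
- Both tubes acquire 20% fewer at a later visit: 80 − 48 = 32, which is 80% of baseline with no biological change.

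**2. Stability of percent of baseline (assumed counts).** The model is net count = Poisson(net + background) − Poisson(background), drawn independently at baseline and post-dose with no true change, 400,000 draws. Ranges, means and SDs below leave out baselines at or below zero. The SAP does not exclude negative ones.

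| Net | Background | Baseline ≤ 0 | 2.5th to 97.5th percentile | Mean (SD) |
|---|---|---|---|---|
| 5 | 5 | 12% | −50% to 700% | 133% (179) |
| 10 | 5 | 1.4% | 13% to 475% | 133% (146) |
| 10 | 20 | 9% | −40% to 800% | 150% (238) |
| 20 | 20 | 0.6% | 23% to 388% | 128% (145) |
| 50 | 20 | about 0 | 57% to 174% | 104% (30) |
| 100 | 20 | about 0 | 72% to 140% | 101% (17) |
| 500 | 20 | about 0 | 88% to 114% | 100% (7) |

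Hand check of the 9%: the difference has mean 10 and variance 30 + 20 = 50, so SD 7.07. With a continuity correction, (0.5 − 10)/7.07 = −1.34, a lower tail of about 0.09.

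**3. The protocol's occupancy figure.** Protocol 3.3.2.2 predicts 18% RO at Cmax for the starting dose and about 10% depletion. With Cmax 0.00707 µg/mL (Table 4), KD 0.218 nM (protocol 1.2.1) and an assumed molecular weight of 150 kDa, C = 7.07/150 = 0.0471 nM. RO = 0.0471/(0.0471 + 0.218) = 17.8%, which agrees with 18%. The 10% depletion cannot be rebuilt from the documents and is taken as stated.

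**4. Occupancy with and without 1B4.** Assume that J11L1 sees only free receptor, that 1B4 sees all LAG-3, and that the J11L1+ count falls in proportion to free receptor. With D for depletion:
- J11L1 relative to baseline = (1 − RO)(1 − D)
- 1B4 relative to baseline = 1 − D
- RO from J11L1 alone = 1 − (1 − RO)(1 − D)
- RO from the ratio = 1 − (J11L1 relative)/(1B4 relative)

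At 18% and 10%: 0.82 × 0.90 = 0.738. J11L1 alone gives 26.2%. The ratio gives 1 − 0.738/0.90 = 18.0%.

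Other pairs (assumed):

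| True RO | Depletion | J11L1 alone | Ratio |
|---|---|---|---|
| 0% | 50% | 50% | 0% |
| 50% | 50% | 75% | 50% |
| 99% | 50% | 99.5% | 99% |

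**The case against.** The strongest reply concerns occupancy. A reader might infer that the SAP prescribes RO from J11L1 alone and so counts depletion as occupancy. The text does not support that. SAP 14.7.2 names 1B4 as the depletion measure in the same sentence, calls model development data driven, and treats the Emax model only as a likely start. A ratio or a joint fit is compatible with it. The SAP's revision table also says that PK/PD dataset specifications now sit in a separate document, where a derivation could exist.

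The clone roles are inferred too. J11L1 can report occupancy only if it competes with the drug, but neither document says that it does. Nor need a count of positive events fall in proportion to free receptor, since a half-occupied cell may still be scored positive. Without that assumption, the 26% does not follow and the proposed ratio is itself only an approximation.

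A reader might also infer that Tables 6.6 and 6.7 overstate occupancy, or that the study cannot separate binding from killing. Neither follows. Those tables contain no RO variable, and both markers are shown and listed, so the ratio can be formed afterwards.

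On the counts, every event number used here is assumed. A proportion below 1% of T cells does not fix the number of events acquired, and absolute values and changes from baseline are already tabulated.

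These replies limit the size and certainty of the problem. They do not remove it. The raw subtraction and percent of baseline are stated rules, the gap for non-positive baselines is real, and no SAP derivation or display links J11L1 to 1B4.

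**Conclusion.** The point holds in two parts of different strength.

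The count derivation is a weakness in what the SAP states. Unequal acquisition passes straight into the result, and small net baselines can give negative or extreme percentages that distort Figures 6.10, 6.11, 6.19 and 6.20. The size depends on counts that the documents do not give: serious at around 10 to 20 net events over a background of 20, small above about 50 to 100.

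The occupancy part is conditional. RO is left without a formula, so confounding with depletion is possible but not prescribed. If J11L1 competes with the drug and its count is proportional to free receptor, J11L1 without 1B4 adds 8 points at the protocol's predicted starting-dose pair (26% against 18%) and half a point at 99% RO with 50% depletion. The bias is greatest at low occupancy, including recovery.

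The consequence is limited. Blood LAG-3 expression is exploratory. The secondary LAG-3+ endpoints come from skin immunohistochemistry, and the Bayesian decision endpoints in SAP 13 do not use blood flow data, so neither is affected. I would class this as a cheap improvement.

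**What to change.** Change SAP 10.3.1, 10.3.2 and 14.7.2 as follows.

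1. Express each tube as percent of its parent CD4+CD45RA+ or CD4+CD45RA- gate, or as cells/µL, before subtracting the FMO value.
2. Define RO(t) = 100 × [1 − (J11L1/1B4 at t)/(J11L1/1B4 at baseline)], or fit both markers jointly in the PK-RO model. State which clone competes with the drug. Keep 1B4 alone as the depletion readout.
3. Show absolute change only, not percent of baseline, when the net baseline is at or below zero or below the FMO value. A minimum number of net baseline events would be a useful addition, because a low background can pass this rule and still be unstable (10 net over 5: 13% to 475%).

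The cost is derivation text and programming, with no new samples, provided parent-gate or volume values are available in the existing flow data. Some RO and percent-of-baseline values will become missing when 1B4+ counts are very low, and the number missing should be reported by dose and visit.
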